from a microbiological perspective. Increased presence of fungi in the airways is associated with Th2 responses in individuals with allergic airway disease [8], suggestive of a causal role, and eosinophils serve important antimicrobial and other regulatory functions [9,10]. Further, a wealth of evidence exists implicating perturbed human microbiota patterns (gut, nasopharyngeal; both bacterial and fungal) as a risk factor for allergy and asthma [11]. Relevant to this proposal, we have found in recent multi-center investigations of the airway microbiome in asthmatic adults that attributes of the airway microbiota differ significantly between those with T2-high versus T2-low asthma [12,13]. Specifically, airway bacterial burden is significantly lower in those with higher T2 airway inflammation. This finding translates into differences in the compositional structure of airway microbiota, including differences in the proportional abundance of specific bacteria, when compared to T2-low asthmatic subjects. Conversely, we have found that T2-low asthmatic subjects harbor higher airway bacterial burden and enrichment in a greater number of different bacteria. Similar trends were observed in recent analysis of induced sputum data from the same subjects in this NHLBI AsthmaNet study [14]. Separately, studies in mice have found that levels of lung inflammatory cytokines (IL-4, IL1- α) correlate with variation in lung microbiota composition and that such interactions likely have bidirectional influence [15].

Given this evidence, we propose a pilot study, leveraging the inherent value in using a specific immunologic intervention, to explore the question: "Does IL-4R α inhibition of T2-mediated immune responses alter the respiratory microbiome within a 4 month period of treatment initiation and follow up, and if so, what are the specific microbiological changes and immune response correlates of these changes?" We will compare pre- and post-dupilumab effects on the respiratory microbiome and determine potential associations between dupilumab-related changes on the microbiome, measured immune responses, and clinical outcome measures. Since dupilumab is systemically administered, we will similarly explore gut microbiome characteristics related to dupilumab-associated changes in clinical and immunologic measures.

III. Objectives

Primary objective

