- To determine changes in the respiratory microbiome after inhibition of IL-4R α in patients with asthma at 1 and 4 months after initiation of treatment

Primary Endpoint (Biological) Measures

- Changes in measured features of respiratory microbiota composition (bacteria, fungi), profiled from induced sputum and nasal samples. Such features include alpha- and beta-diversity ecologic measures, which reflect microbiota composition within and between-samples, respectively. Examples include Shannon and phylogenetic diversity indices, richness and evenness metrics (alpha-diversity), and Unifrac or Bray-Curtis distance measures to compare across samples (beta-diversity). Additional readouts of the microbiome to be analyzed include bacterial burden by quantitative PCR, abundance profiles of microbial community members, and microbial gene functions annotated from metagenomic sequence data.
- Changes in similarly calculated measures of microbiota composition in stool samples collected before and after dupilumab initiation (baseline and 4 months)

Secondary Objectives

- To examine correlations between changes in measured features of the respiratory microbiome and changes in blood and airway immune responses with dupilumab treatment
- To determine relationships between changes in measured features of the respiratory microbiome and changes in clinical outcome measures including lung function and asthma control scores with dupilumab treatment
- To determine if combinations of correlated immune markers and microbiota patterns predict improvement or lack of improvement in clinical outcome measures related to dupilumab treatment
- To explore associations between gut microbiome composition, aeroallergen sensitization, severe asthma features and response to dupilumab treatment.
- To explore the relationship between gut microbiota compositional, the intestinal metabolome, and response to dupilumab.
- To explore and compare dupilumab-related, compartment-specific changes in the respiratory microbiome to that observed in the gut microbiome

Secondary Endpoint (Clinical) Measures

Clinical outcome measures (all visits)

- Spirometry: FEV1/FVC ratio, FEV1, and FVC pre- and post-bronchodilator.
- Fractional exhaled nitric oxide (FeNO)
- Asthma Control Test [16]
- Asthma quality of life questionnaire (mini-AQLQ) [17]
- SNOT-22 [18, 19]
- Asthma medication use and dosage
- Asthma exacerbations requiring at least 3 days of oral corticosteroids

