Dupilumab-eligible severe asthma patients will be identified and recruited from asthma and allergy clinics at the University of Michigan. Severe asthma patients are seen and cared for by Pulmonary and Allergy faculty at two main outpatient clinic locations. All severe asthma patients who meet clinical prescribing criteria for dupilumab are considered eligible and will be recruited for this study. The study coordinator and/or physician investigator will meet with subjects to provide information about the study and invite them to participate in this 3-visit study occurring over a 4-month period. We will enroll 15 severe asthma patients who complete all 3 visits. The funder of the grant for this project (Regeneron) will provide dupilumab for this study.

Inclusion criteria:

1. Adults ages 18 or older with physician-diagnosed/-managed severe asthma who are clinically eligible for dupilumab (clinical criteria below).
2. Current treatment with a medium-to-high-dose inhaled glucocorticoid (fluticasone propionate at a total daily dose of ≥ 440 μ g or equipotent equivalent) plus up to at least one additional controller (e.g., a long-acting β 2-agonist or leukotriene receptor antagonist)
3. Eosinophilic asthma phenotype (blood eosinophil level >300) or asthma requiring daily oral corticosteroids
4. Asthma that is uncontrolled, as defined by a score on the Asthma Control Test of 19 or lower, OR a worsening of asthma in the past year that led to an asthma hospitalization, ED visit, or 3 days of oral corticosteroids
5. Severity of asthma that, in the opinion of the subject's asthma care specialist, requires dupilumab for control

Exclusion Criteria:

1. Patients with diagnosis of other chronic lung diseases (e.g. COPD, idiopathic pulmonary fibrosis, Churg-Strauss syndrome, ABPA, etc.)

2. Current smoker or reported smoking within 1 month of the screening visit (tobacco or any inhaled recreational product)
3. Greater than 10 total pack-year of cigarette smoking history
4. Treatment with oral corticosteroids for an asthma exacerbation 1 month prior to screening or during the screening period
5. Use of any biologic therapy for asthma within the past 3 months
6. Respiratory or GI illness within 1 month prior to screening or during the screening period
7. Treatment with antibiotics for acute infections within six weeks prior to screening or during the screening period.
8. Pregnancy at enrollment or during the study
9. Known hypersensitivity to dupilumab or its excipients

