Procedures

The following lists the study procedures subjects will be asked to perform. Some are indicated only for visit-specific criteria as detailed in subsequent sections and summarized in **Table 1**.

1. Full and abbreviated medical history intake and physical exam by study physician
2. Review of inclusion/exclusion criteria at each visit to ensure criteria still met.
3. Questionnaires
 - Asthma Control Test (ACT; 5 items; [Appendix 1](#); [16])
 - Mini-Asthma Quality of Life Questionnaire (mAQLQ; 15 items; [Appendix 2](#) [17])
 - SNOT-22 (22 items; [Appendix 3](#) [18,19])
3. Blood draw (for clinical lab tests and plasma tube for [name] lab processing)
4. Nasal epithelial lining fluid (NELF) collection ([Appendix 4](#))
5. Spirometry pre- and post-albuterol administration
6. Oral rinse/tongue scraping prior to sputum induction
7. Sputum induction
8. Stool collection (two samples: one for metabolite analysis- EasySampler kit, and one for microbial using Zymo; [Appendix 5](#))

Table 1. Schedule of visits and procedures (V1-V3 conducted at Medical Clinical Research Unit)¹

Visit	Screening	V1	TC1 ⁴	V2	TC2 ⁴	V3
		2-4 wks post-screen	Brief Phone call	1 month post-V1	Brief phone call	4 months post-V1
Dupilumab treatment status	No drug	Start drug	On drug	On drug	On drug	On drug
Procedures						
COVID-19 testing per Michigan Medicine policies²		X		X		X
Review of inclusion/exclusion criteria ³	X	X		X		X
Full or short history/exam ³		X		X		X
ACT questionnaire		X		X		X
SNOT-22 questionnaire		X		X		X
Mini-AQLQ		X		X		X
Exhaled nitric oxide (FeNO) ³		X		X		X
Nasal epithelial lining fluid (NELF) collection ⁴		X		X		X
Spirometry pre- and post-bronchodilator		X		X		X
Blood draw/Phlebotomy lab		X		X		X
Complete blood count with differential		X		X		X
Serum total IgE		X				
Respiratory Allergen panel (specific IgE tests)		X				
Plasma collection for research lab assays		X				X
Oral saline rinse/tongue scraping		X		X		X
Sputum induction		X		X		X
Stool collection materials (distribution, instruction)		X				X
Administer/provide dupilumab doses at study visit		X		X		X

1 Subjects should not eat for at least 4 hours prior to visits to limit intolerance of spirometry or sputum induction due to a full stomach. Subjects should not have caffeine (as is in coffee, teas, colas, and chocolate) for at least 6 hours prior to visits, for accuracy of measurements in lung function tests.

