2 Per current policy (as of Jan 2021) at Michigan Medicine, subjects must undergo COVID-19 testing (nasal swab) and have a negative test within 96 hrs prior to aerosol-generating procedures. Testing will be arranged by study team for each visit. If the test is positive for COVID-19 or test result is not available, the study visit will need to be rescheduled.

3 A physician must see the subject at each visit.

4 FeNO measurement and NELF collection should be performed before spirometry and sputum induction.

5 Brief telephone call by study coordinator to (a) ensure subjects are self-administering dupilumab doses between study visits, (b) address any interim questions, and (c) remind them of upcoming in-person study visit. The TC encounters are important to maintain contact with subjects and ensure adherence and follow through during the course of the study

V. VISIT-SPECIFIC DETAILS

SCREENING.

This is the first encounter with eligible patient at which time information about the study is provided by the study coordinator. This may occur by phone or email. A short list of questions will be asked to confirm eligibility. If on the basis of this screen, an individual is eligible to participate the study, a copy of the informed consent will be provided for subject review prior to Visit 1. Signed informed consent will be collected at Visit 1. (*Anticipated total time by study coordinator: 10 minutes.*)

VISIT 1.

Preparations

1. V1 should be scheduled within 2-4 weeks after screening. Subjects will be reminded by study coordinator to take their usual asthma treatments as prescribed including on the day of the visit. Coordinate V1 scheduling with physician investigator availability to perform history and physical exam.
2. Coordinate with Research Pharmacy preparation of dupilumab syringe for administration to subjects after completing all visit testing. Ensure appropriate orders are submitted in advance of V1 date. Also ensure subject will have subsequent doses of dupilimab prepared for self-administration at home between V1 and V2.
3. Notify [name] in [name] Lab ([name]) the day before the visit so that the lab can prepare necessary materials to collect and process samples. Ensure a bucket of ice is available to place collected samples for transport to [name] lab.

Visit procedures

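### The visible schedule does not secure a stool sample from before the first dupilumab dose, which the gut part of the primary endpoint needs

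*Combined protocol and SAP*

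**What the plan says.** - **Endpoint.** Section III lists, under the primary endpoint measures, changes in microbiota composition in "stool samples collected before and after dupilumab initiation (baseline and 4 months". The primary objective itself names only the respiratory microbiome, and Section II describes the gut work as exploratory: "we will similarly explore gut microbiome characteristics related to dupilumab-associated changes in clinical and immunologic measures".
- **Design.** One group, compared before and after treatment. Section IV sets the target: "We will enroll 15 severe asthma patients who complete all 3 visits".
- **Table 1.** The stool row reads "Stool collection materials (distribution, instruction". It is marked at V1 and V3, and not at screening or V2. V1 is the column in which treatment starts.
- **Before V1.** Screening may take place by phone or email and mentions no kit. On the interval: "V1 should be scheduled within 2-4 weeks after screening". The screening text has consent signed at V1; Visit 1, item 5 allows for it having been obtained earlier.
- **First dose.** Visit 1, Preparations item 2 says "Coordinate with Research Pharmacy preparation of dupilumab syringe for administration to subjects after completing all visit testing", and Visit 1, item 8 places the first injection in that visit once its procedures are done.
- **Visit 2.** The preparations provide for a stool specimen being brought in; the Visit 3 preparations repeat the sentence. At the end of Visit 2 the subject receives a kit to be kept until the day of Visit 3.
- **Visit 3.** A subject who has not yet returned the sample is reminded to do so within 1-3 days.
- **Interval from V1 to V2.** Section V gives it as at least 4 weeks (Visit 1, item 9) and as approximately 4 weeks (Visit 2, Preparations item 1).
- **Appendix 5.** The procedures list in Section IV points to it for stool collection. Only its title is in the text available.

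**The concern.** With no control arm, a change in the gut microbiome can be seen only against each subject's own pre-dose stool. If the first stool is collected after the loading dose, the analysis compares two on-drug samples and labels the difference a before-after change. Stool is collected for both microbial and metabolite assays, so composition, diversity and fecal metabolites would all be affected for that subject. A missed pre-dose stool cannot be collected later.

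**Working it through.** The plan gives no figure to reproduce: the 15 has no calculation behind it. The check is a timeline, followed by an illustration of size.

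**1. When can the subject first hold a kit?** The visible contacts before the first dose are screening (no kit mentioned), the arrangement of COVID-19 testing (no kit mentioned) and V1 (kit handed out). The earliest visible supply is therefore at the dosing visit.

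**2. What can a kit supplied at V1 yield?**
- Stool passed on site before the injection: pre-dose.
- Stool collected at home: post-dose.

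The rule that dosing follows all visit testing does not separate these cases, because handing over the kit and instructing the subject already completes the Table 1 row as labelled.

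**3. How late could a home sample be?**
- If the Visit 3 reminder window were applied to V1 (an assumption; none is stated there): 1-3 days after the first dose.
- If brought to V2: about 4 × 7 = 28 days. This is not a ceiling, since V2 is also described as at least 4 weeks after V1.
- Injections before such a sample: the V1 dose, with or without the home dose about 2 weeks later, so 1 or 2.
- Span left if the sample is passed at V2: V3 at 4 months minus V2 at 1 month = 3 of the intended 4 months, on drug at both ends.

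**4. Baseline beside the 4-month sample.**

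| | Baseline stool | 4-month stool |
|---|---|---|
| Kit supplied at an earlier visit | not in visible text | yes, V2 |
| Collection day stated | not in visible text | yes, day of V3 |
| Late-return instruction | not in visible text | yes, 1-3 days |

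**5. Table 1 beside the Visit 2 text.** As labelled, the row distributes materials at V1 and V3. The text distributes the V3 kit at V2, so label and marks do not both fit. Read as collection time points, V1 and V3 match the baseline and 4 months of Section III, but then no visible step supplies the baseline kit.

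**6. Size.** One subject without a pre-dose stool is 1/15 = 6.7% of the intended gut pairs. The share affected is not in the documents, so what follows is illustration only. It uses a paired t-test with assumed two-sided α = 0.05 and 80% power. Power is P(|T| > t(0.975, n−1)), where T is noncentral t with n−1 degrees of freedom and noncentrality δ√n, and δ is the standardized paired change.

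| Valid pairs | Detectable δ |
|---|---|
| 15 | 0.78 |
| 12 | 0.89 |
| 10 | 1.00 |
| 8 | 1.16 |

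If post-dose baselines are kept instead, and a share f of subjects already shows a fraction r of the effect, the mean change becomes δ(1 − f·r). This assumes the SD of the change stays the same. With n = 15, δ = 0.78 and f = 0.5:
- r = 0.25: factor 1 − 0.125 = 0.875, power falls from 80% to about 69%.
- r = 0.50: factor 1 − 0.25 = 0.75, power falls to about 56%.

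Both f and r are assumptions.

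**The case against.** The strongest reply is that the timing may be settled in Appendix 5, which is where one would expect it and which is not visible. That stands: nobody can say from this text that the plan lacks a rule. A related reply is that the Table 1 row may be meant to mark stool time points. Section III already requires pre-treatment stool, and dosing follows the visit's testing, so the intended order would be right. That reading is reasonable. It still leaves open how a subject comes to hold a kit before V1, and the label as printed says something else.

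Four stronger readings are tempting and should not be drawn.

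- A reader might infer that baseline stools will be post-dose. The text allows on-site collection before the injection, and Appendix 5 may require pre-dose collection.
- A reader might take the absence of a stool step from the V1 procedure sequence as proof that none is collected then. The V3 sequence has no stool step either, although a V3 stool is certainly due. The V1 laboratory-notification item ("Ensure a bucket of ice is available to place collected samples for transport to" the laboratory) names no specimen type, so its silence on stool also shows little.
- A reader might treat the Visit 2 sentence as evidence that the first stool is expected at V2. It is identical to the Visit 3 sentence and may be carried-over text.
- A reader might conclude from the enrolment target that lost stool pairs will not be replaced. The target counts subjects who complete three visits, but nothing says whether a subject without stool counts as complete.

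Scope also limits the point. This is a pilot with exploratory hypotheses, the primary objective is respiratory, and the V1 sputum and nasal samples precede dosing.

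**Conclusion.** The point holds in a limited form and should be fixed. The gut part of the primary endpoint needs pre-dose stool. The visible schedule first hands out stool materials at the visit where dosing starts and does not say that the sample must come before the injection. Followed as written with home collection, it gives an on-drug baseline in a study whose only comparator is that baseline. Table 1 and the Visit 2 text also disagree on when kits are handed out.

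The number of subjects affected and the dilution of the gut effect cannot be derived. What can be said is 6.7% of the intended pairs per subject, a delay from the day of dosing up to about 4 weeks or slightly more, and at that far end about 3 of the 4 months remaining. The conclusion assumes that Appendix 5 does not already fix pre-dose collection. If it does, what remains is a mismatch between Table 1, the visit text and the appendix. The respiratory endpoint is untouched on any reading.

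**What to change.** 1. Supply the baseline kit after consent and before V1, with an instruction to collect before V1 and return the sample at V1. The 2-4 weeks (14-28 days) from screening to V1 leave time for this. The COVID-19 testing contact ("Testing will be arranged by study team for each visit") can carry a reminder, though it falls close to the visit. Reconcile the screening text on consent with Visit 1, item 5, which already allows earlier consent.
2. Record the stool collection date and time beside the first-dose date and time.
3. Define baseline stool for the gut before-after analysis as stool collected before the first dose, and report later samples separately. This is a sample-timing and analysis rule and does not change dosing; a subject without a pre-dose stool simply has no baseline in that analysis.
4. Split the Table 1 stool row into distribution (before V1, and V2) and collection (V1, V3).
5. State which time point a stool brought to V2 represents, or remove the sentence if it is carried over.
6. If Appendix 5 already requires pre-dose collection, align Table 1 and the Visit 1 text with it.

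The cost is kit mailing, an earlier consent contact for some subjects (screening is otherwise a 10-minute remote contact), and wording changes. No samples, visits or patients are added. Item 3 can reduce the number of gut pairs, which is why item 1 matters more.
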